# 5.5 Objectives and hypothesis

## 5.5.1 General Objective

To evaluate the safety and tolerability of the ophthalmic gel PRO-167 on the ocular surface.

#### 5.5.2 Specific objectives

- Describe the safety of the ophthalmic gel PRO-167 by means of the density of goblet cells
- Describe the safety of the ophthalmic gel PRO-167 by means of changes in ocular surface stains.

- Describe the safety of the ophthalmic gel PRO-167 by means of changes in intraocular pressure.
- Describe the safety of the ophthalmic gel PRO-167 by means of changes in laboratory tests.
- Describe the safety of the ophthalmic gel PRO-167 by means of changes in vital signs.
- Describe the safety of the ophthalmic gel PRO-167 by means of changes in visual ability.
- Describe the safety of the ophthalmic gel PRO-167 by means of changes in the time of tear rupture.
- Describe the safety of the ophthalmic gel PRO-167 by means of changes in the ocular comfort index.
- Describe the safety of the ophthalmic gel PRO-167 by means of changes in the posterior segment.
- Describe the safety of the ophthalmic gel PRO-167 by means of changes in ophthalmological signs and symptoms.
- Describe the safety of the ophthalmic gel PRO-167 when assessing the integrity of the anterior segment by means of the green lysine stain.
- Describe the safety of the ophthalmic gel PRO-167 by means of the presentation of adverse events.

# 5.5.3 Hypothesis

*Ha* Ophthalmic gel PRO-167 presents a safety and tolerability profile similar to the comparator in healthy subjects.

Ho Ophthalmic gel PRO-167 presents a safety and tolerability profile different from the comparator in healthy subjects.

# 5.6 Design and plan of the study

Clinical trial, phase I, controlled, parallel groups, double blind randomization, exploratory.

# 5.6.1 Discussion of the study design

The design of the study (clinical trial) is considered the highest quality standard in the data when it is sought to explore the effect of an intervention. The phase of pharmacological development (phase I) corresponds to the objective of the study which is to assess safety and tolerability, so that the intervention time is short and the sample size required is less than that of a clinical efficacy trial. The presence of parallel groups allows the comparison between the intervention groups on the outcome variables. Blinding and randomization allows to reduce biases that are incurred with other designs, e.g. Selection bias, evaluation bias, among others.

# 6. Material and methods. Participants, interventions and variables

# 6.1 Study Center

The present study will be performed in ophthalmology offices duly equipped and registered for their proper functioning. According to the needs of the sponsor, these may be private or public, be attached to a hospital or clinic or be independent.

## 6.1.1 Organization of the center

Each study center will have a principal investigator (PI). The PI is the ophthalmology specialist in the clinical study.

The PI is responsible for forming a multidisciplinary research team to carry out the clinical study according to protocol, under its scientific guidance. It is the prerogative of the IP the design of the organization of its center and the selection of the personnel that will perform the functions. However, the minimum organization of the research team requested by the sponsor requires the figure of sub-researcher, study coordinator and pharmacist. (See Figure 1 Minimum organization of the center)

Any person to whom the PI designates, under his / her responsibility, a part of the follow-up of the study (co-investigator, under-researcher, nurse, etc.) or a specific function of participation in the study (pharmacist, administrative assistant, study coordinator, etc.) should appear in the "Delegation of Responsibilities" format.

[figure not shown]

Figure 1 Minimum organization of the center

The "Delegation of Responsibilities" and the "Organizational Chart of the Center" must be delivered to the sponsor before the start of the study and updated if the members or their responsibilities are changed.

# 6.1.2 Documentation to be delivered to the sponsor

The PI must deliver to the sponsor, before the start of the study:

- Curriculum vitae updated, in Spanish, dated and signed (maximum 10 pages), of the IP and the staff that integrates its organizational chart of the center.
- Copy of IP academic certifications (degree certificate and specialty diploma in ophthalmology, federal professional certificates)
- Copy of academic certifications of the maximum degree obtained, from each one of the members of your research team, that cover their capacity to perform the delegated functions.

- Copy of operating notice or similar issued by corresponding regulatory entity (When applicable)
- Certificate of good clinical practice in force. If the issuing institution does not specify the validity period in the certificate, the date of issue of the certificate must not exceed one year

#### 6.1.3 Closure of the center

The closing of the center will be carried out once the last visit of the last included subject previously agreed between the sponsor and the IP has been made. The closing process will be according to the internal operating procedures of the sponsor.

It is the prerogative of the sponsor to prematurely close a study center, it must inform the IP the reasons for the closure.

# 6.2 Eligibility criteria

#### 6.2.1 Inclusion criteria

- Signed informed consent.
- Systemically and ophthalmologically healthy subjects evaluated during the clinical history.
- Age between 18 to 45 years.
- Both genders.
- Blood tests [complete blood count (BHc), three element blood chemistry (QS) and liver function tests (PFH)] within normal parameters specified by the reference laboratory with a lower and upper margin of 10%.
- Vital signs within normal parameters.
- Visual capacity 20/30 or better, in both eyes.
- Intraocular pressure ≥11 and ≤ 21 mmHg.

#### 6.2.2 Exclusion criteria

#### 6.2.2.1 General criteria

- Subjects with a history of hypersensitivity to any of the components of the research products.
- Subject users of topical ophthalmic medications of any pharmacological group.
- Subject users of medication by any other route of administration.
- Pregnant or lactating women.
- Women without a history of hysterectomy, oophorectomy, who do not ensure a hormonal contraceptive method or intrauterine device during the study period.
- Subjects with participation in clinical research studies 90 days prior to inclusion in the present study.
- Diagnosis of liver disease or elevation to three times the normal upper value of any of the following liver enzymes: aspartate transferase (AST), alanine transferase (ALT) or bilirubin.
- Inability to attend or answer the evaluations made in each of the visits.
- Positive smoking (specified as cigarette consumption regardless of amount and frequency)
- Positive alcoholism (specified as the consumption of alcoholic beverages, regardless of quantity and frequency, during the study intervention period).

Version: 1.0

#### - Contact lens users.

#### 6.2.2.2 Medical and therapeutic criteria

#### 6.2.3 Elimination criteria

- Withdrawal of the consent letter under information.
- Presentation of a serious adverse event.
- No tolerability or hypersensitivity to any of the compounds used during the tests (fluorescein, green lysine, tetracaine)
- No tolerability or hypersensitivity to any of the investigational drugs.
- Adherence <50% determined by the diary of the subject.

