#### 6.3.2.1 Procedure to monitor adherence

Before delivering the medication to the research subject, the pharmacist must weigh the tubes to be delivered. After the return of the medication by the subject will also carry out the weighing. Guidelines to follow for weighing:

- o The pharmacist will use the scale provided by the sponsor
- o Place the tube in the center of the balance. You will get the result of the measurement.
- o It will remove the tube from the balance and put it back, confirming that the measurement is the same. If it is different, it will weigh one more time and take the average of the 3 measurements
  - o Record the result in the log and the CRF provided by the sponsor

Adherence to the intervention will be calculated considering: the weight of the empty tube, the weight of the strip, the weight of the tube with the content, the calculation of the total gel to be applied during the entire intervention time and the total weight of the applied gel . The following simplified formula will be used:

$$Ad = \frac{\left(P_i - P_f\right)100}{P_T}$$

Where:

Ad = adhesion

 $P_i$  = weight of the tube delivered to the subject at the start

 $P_f$  = weight of the tube returned by the subject

 $P_T$  = weight of the posology indicated for the intervention

$$P_T = (P_g)G$$

where:

 ${\it P_g}$ = weight of a 1 cm strip of the intervention, determined by the research and development department

G = number of applications indicated for the intervention

Adherence will be estimated at each visit where the research subject returns the intervention. Only tubes without apparent physical damage will be considered for the calculation. This result will allow the PI to determine if the subject continues in the study according to the stipulations of the elimination criteria.

The evaluation of the adherence by means of the diary of the subject will be carried out in the following way:

$$Ad = (A_r)100/A_i$$

Ad = Adhesion

 $A_r$ = Registered applications

 $A_i$ = Applications indicated for the intervention

The final (overall) adhesion will be determined by the average of the adherence of each of the visits.

It will not be considered for the calculation of final adherence if the subject did not return the tube in two subsequent visits.

Sophia Laboratories A.S. of V.C.

Version: 1.0

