#### 6.4.1.2 Primary outcome variables of tolerability

- Burning
- Foreign body sensation
- Itching
- Eye comfort index

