## 6.5 Timeline and study diagram

Procedures	scrutiny	Basal visit	Visit 1	Final visit	Call Security
Procedures		Day 0	Day 3 ± 1	Day 11 ± 1	Day 13 ± 1
CI signature	Х				
clinic history	Χ				
Ophthalmological clinical history	Х				
Laboratory sample taking	Χ			Χ	
Laboratory tests review		Х			Х
Pregnancy test	Χ			Χ	
Eligibility criteria	Х	Xa			
Assignment		Χ			
Delivery of intervention		Х	Х		
Return of intervention			Χ	Χ	
Adherence evaluation			Х	Х	
Adverse events			Х	Χ	Χ
Intraocular pressure	Х	X 	Х	Х	
Visual ability	Χ	X 	Χ	Χ	
TRL	Х	X 	Х	Х	
Epithelial defects (TF and TVL)	Χ	X 	Х	Χ	
Eye signs and symptoms	Х	X 	Х	Х	
Posterior Segment	Χ	X 		Χ	
Vital signs	Х	X 	Х	Х	
Ocular Comfort Index		Х		Х	
Goblet cell density (cytology by impression)		Х		Х	
Daily delivery of the subject		Χ	Х		
Return / Evaluation of the subject's Journal			Х	Х	
Delivery Quality Questionnaire		Χ			
Return and Evaluation of the quality questionnaire				Х	
Continuity evaluation of the subject		Х	X	X	

a The eligibility criteria will be completed with the revision of the laboratory exams. 1 These measurements may be taken from the result of the screening visit, if it does not exceed the previous 7 days. It is the prerogative of the PI to decide whether to repeat the measurements at the baseline visit.

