#### 8.1.1 Strategies to complete the follow-up

- You will be clearly informed of the importance of the study and the benefits that the population will obtain from the results of the study.
- Transportation assistance will be provided in order for the participant to attend their visits.
- Calls, messages or a printed calendar will be made in order to remind the participant of their appointments and the activities that will be carried out, in addition to the estimated duration of the same.
- In case the participant does not attend his appointment, the research center must make a call to know the reason and try to arrange a new appointment within the established window period or an unscheduled appointment.
- In case it is not possible to make an appointment, it will be asked about the presence of adverse events and the reason for leaving the study, as minimum data.

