#### 8.3.3 Population analysis and management of missing data

An analysis will be carried out by intent to treat where the data of the participants that have fulfilled two visits will be included (Basal Visit and visit 1).

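### No early-termination assessment is planned, so a subject eliminated before Day 11 has no post-baseline goblet cell density or eye comfort index, and no missing-data rule covers the gap

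*Combined protocol and SAP*

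**What the plan says.** Section 6.2.3 lists the grounds for elimination. They include "No tolerability or hypersensitivity to any of the investigational drugs", "Presentation of a serious adverse event" and "Adherence <50% determined by the diary of the subject". Section 6.3.2.1 shows that elimination means leaving the study and not only stopping the gel. It says of the adherence figure: "This result will allow the PI to determine if the subject continues in the study according to the stipulations of the elimination criteria".

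"Eye comfort index" is a primary tolerability variable (6.4.1.2), and goblet cell density is a primary safety variable (6.4.1.1). In the 6.5 timetable, the row that begins "Goblet cell density (cytology by impression" is marked at the baseline and final visits only, and so is the comfort index row. Sections 6.4.4, 6.5.1.3 and 6.5.1.4 agree that Visit 1 has neither and the final visit has both. Staining and symptom scores are taken at Visit 1 (Day 3 ± 1) and at the final visit (Day 11 ± 1). There is no early-termination visit.

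Section 8.1.1 deals with missed appointments. The centre telephones and tries to arrange a new or unscheduled appointment, for which no procedures are listed. If that fails, "it will be asked about the presence of adverse events and the reason for leaving the study, as minimum data".

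Section 8.3.3 states: "An analysis will be carried out by intent to treat". It takes in subjects who completed the baseline visit and Visit 1. Its heading mentions missing data, but the text gives no rule. Section 8.3.1 also limits the analysis to adherence above 60%, reports adverse events for everyone randomised, and calls the gel safe and tolerable if no primary variable differs clinically and statistically from the comparator.

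**The concern.** Intolerance is both what the trial sets out to measure and a reason to leave before two of the measurements are taken. Followed as written, the plan loses those values because of the outcome itself. Choosing a different analysis set cannot recover them. A subject stopped between Visit 1 and Day 11 is inside the 8.3.3 population but has nothing to contribute to either comparison.

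The direction matters because 8.3.1 treats absence of a difference as success. If the subjects who tolerated the gel least are unmeasured, the arms look more alike on these two variables. With 12 per arm, one to three such subjects are a visible share of the data.

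**Working it through.** **The plan's own allowance for losses (6.6.1).** 19 / (1 − 0.20) = 23.75, rounded up to 24, or 12 per arm. This reproduces the stated total. The base of 19 cannot be checked because no value of delta is given, but nothing here depends on it. A 20% loss is 12 × 0.20 = 2.4 subjects per arm.

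**A subject stopped on Day 6, between the visits.**
- Goblet cell density and comfort index: baseline only.
- Symptom and staining scores: the last are from Day 3 ± 1.
- Post-application diary symptoms (6.4.3.9): recorded up to the stop.
- Adverse events: recorded and reported.
- 8.3.3 population: included, with no rule for the two missing values.
- Adherence filter: dosing starts on Day 1, four times daily for 10 days, so 40 applications. Full use through Day 6 is 24 / 40 = 60%, which is not above 60%. If adherence is counted over the full course, the subject is excluded under 8.3.1 even if measured.

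A subject stopped before Visit 1 falls outside the 8.3.3 population altogether.

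**How often this could arise.** The documents give no elimination rate. Section 6.6.1 expects bad tolerance in no more than 10%. Taking that as an assumed elimination rate q, with a range of 5% to 25%:

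| q | expected per arm, 12q | at least one in 12, 1 − (1 − q)^12 | at least one in 24, 1 − (1 − q)^24 |
|---|---|---|---|
| 5% | 0.6 | 46% | 71% |
| 10% | 1.2 | 72% | 92% |
| 25% | 3.0 | 97% | 99.9% |

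**What it does to a mean (invented scores, higher is worse).** Three of 12 stop with an index of 60 and nine score 10. The full arm mean is (3 × 60 + 9 × 10) / 12 = 22.5. The recorded mean is 90 / 9 = 10.0, the same as a comparator arm with every score at 10. The 12.5-point difference is not seen.

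**What it does to the planned test.** With all 24 of those values collected, the exact two-sided Mann-Whitney p is 2 × C(12,3) / C(24,3) = 2 × 220 / 2024 = 0.217. The tie-corrected normal approximation gives 0.070. Neither reaches 0.05.

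A simulation of 12 against 12 (4,000 runs, normal data, completers not differing, exact Mann-Whitney at 0.05, losses in one arm only) gave these proportions significant:

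| missing in one arm | completers only | missing ranked worst |
|---|---|---|
| 1 | 4.1% | 4.1% |
| 2 | 4.1% | 7.4% |
| 3 | 4.9% | 11.9% |
| 4 | 4.8% | 22.2% |
| 5 | 4.8% | 36.3% |

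At one or two losses the test hardly moves. What suffers there is the descriptive and clinical comparison, which 8.3.1 also relies on.

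**The case against.** The strongest reply is that the trial does not lose sight of intolerance. Presence of adverse events is itself primary and is reported for all randomised subjects, and events are followed to their outcome (9.3.1.2). The diary records burning, foreign body sensation, itching and red eye after each application. An imbalance in stops for intolerance would therefore remain visible to the 8.3.1 rule. This stands, and it limits the point to two primary variables plus the late values of the symptom and staining scores.

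The loss is also inferred from silence. Nothing forbids assessing an eliminated subject, and 9.3.1.3 leaves withdrawal or continuation after an event to the investigator. That is fair, but an assessment that is neither scheduled nor required will be done unevenly, if at all.

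Three stronger readings are tempting, and the documents do not support them:
- A reader might infer that these variables are never measured in low adherers. Adherence is judged when tube and diary come back, at Visit 1 and the final visit, and both variables are scheduled at the final visit. Low adherence found there leads to exclusion by the 60% filter and not to a missing measurement. Nor does anything show that low adherers fared worst.
- A reader might take 8.1.1 to say that adverse events and the reason are all that is collected from anyone who leaves. That section concerns missed visits, tries another appointment first, and sets a minimum.
- A reader might infer that the missing values would overturn the conclusion. The three-of-12 example is not significant even when complete.

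**Conclusion.** The point holds in this limited form. A subject eliminated before Day 11, for example for intolerance or a serious adverse event, has no post-baseline goblet cell density or comfort index under the schedule, and no rule says how the analysis treats that. The comparisons of these two variables are then made mainly in those who tolerated the gel, which leans towards the conclusion the plan counts as success.

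The direction follows from the documents, provided that stops are linked to poorer outcomes. The size does not: it depends on how many stop and in which arm, and neither is given. At the assumed 10%, about one subject per arm is affected and the significance test barely changes. The effect on the test becomes material only with about three or more losses concentrated in one arm. This is worth correcting because it is cheap, not because it is shown to change the result.

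**What to change.** Leave the rules on who stops treatment as they are. Make these changes:

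1. In 6.2.3 and 6.5, state that a subject eliminated before Day 11 who has not withdrawn consent is asked to have the scheduled final-visit assessments at the time of stopping. These are the comfort index, symptom scores, signs, visual capacity, laboratory sample, and return of tube and diary, followed by the safety call. Cytology, staining and pressure are added where the investigator judges them feasible, and not where the subject did not tolerate the agents used. Intolerance of fluorescein, green lysine or tetracaine is itself a ground for elimination, and these procedures use those agents or a topical anaesthetic.
2. In 8.3.3, use these as the subject's end-of-treatment values in the intent-to-treat analysis regardless of the 60% adherence filter.
3. Reconcile the 50% diary threshold in 6.2.3, the 60% filter in 8.3.1 and the population in 8.3.3. Say what happens to a subject stopped before Visit 1.
4. Add a sensitivity analysis that gives the worst rank to subjects stopped for intolerance or a serious event whose values are still missing.

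The cost is wording in the protocol and case report form. The procedures are already planned and only move earlier. The drawback is that measurement time differs for a few subjects, which the report should state.

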#### 6.2.4 Identification of the subject

The patients of the study will be identified by a number and the initials of their name.

The initials of the study subject will be obtained starting with the first letter of the name, followed by the first letter of the first surname and the first letter of the second surname, obtaining maximum three letters, in case the person has two names or a compound surname the first letter will always be used.

[figure not shown]

# Example:

Version: 1.0

#### 6.3 Intervention

# 6.3.1 Managed treatments

# 6.3.1.1 Treatment under study

#### PRO-167

- o Active ingredients: Dexpanthenol 5%
- o Pharmaceutical form: Ophthalmic gel.
- o Prepared by: Sophia Laboratories A.S. of V.C.
- Posology: a strip approximately 1 cm long, 4 times a day during the waking period, in the bottom of the right eye sac.
- Description of the formulation: transparent gel, free of visible particles.
- o Description of the packaging: sterile multi-dose tube, low density polyethylene polyethylene and aluminum with high density polyethylene lid.

Table 3. Quali-quantitative formulation of PRO-167

Type of agent	Amount mg/mL	Function
Dexpanthenol	50.0	Active principle (lubricant)
Boric acid	2.00	Active principle
Sodium Borate decahydrate	without showing	additive
Polysorbate 80	without showing	additive
Sorbitol	without showing	additive
Potassium chloride	without showing	additive
Sodium chloride	without showing	additive
Magnesium Chloride hexahydrate	without showing	additive
Water for the preparation of injectables c.b.p.	1.00	Vehicle

Quali-quantitative formulation of the product under investigation PRO-167. The concentration of the active principles is shown, as well as the substances that act as a buffer additive.

#### 6.3.1.2 Reference treatment

# Corneregel®

- Active ingredients: Dexpanthenol 5%
- o Pharmaceutical form: Ophthalmic gel
- Prepared by: Bausch & Lomb.
- Posology: a strip approximately 1 cm long, 4 times a day during the waking period, in the bottom of the right eye sac.
- o Description of container: sterile multi-dose tuve

#### 6.3.2 Strategies to improve adherence and procedure to monitor adherence

- 1. Each visit the research subject will return the assigned tube in order to evaluate the adherence by weigh
- 2. Direct questioning by the PI about the application of the intervention.

- 3. At the discretion of the IP, messages may be sent or reminder calls made.
- 4. Delivery of a printed chronogram specifying the date of the visit and its activities
- 5. Journal of the subject.

